7.2.8 Serious Adverse Events

AEs are classified as serious or non-serious. An AE or ADR is considered “serious” if, in the view of either the investigator or Sponsor, it results in one of the following outcomes:

- Death
- Life-threatening AE (i.e., the subject was at immediate risk of death from the AE as it occurred. This does not include an event that, had it occurred in a more severe form or was allowed to continue, might have caused death)
- In-patient hospitalization or prolongation of existing hospitalization
- Persistent or significant disability or incapacity or substantial disruption of the ability to conduct normal life functions
- A congenital anomaly or birth defect
- An important medical event

Important medical events are those events that may not be immediately life-threatening or result in death or hospitalization but are clearly of major clinical significance. They may jeopardize the subject and may require intervention to prevent one of the other serious outcomes noted above. For example, drug overdose or abuse, blood dyscrasias, a seizure that did not result in in-patient hospitalization or intensive treatment for allergic bronchospasm in an emergency department would typically be considered serious.

7.2.9 Investigator Responsibilities for Reporting Serious Adverse Events

The investigator must immediately report to the Sponsor all SAEs, regardless of whether the investigator believes they are related to SM.

All SAEs must be reported to the Drug Safety Team within 24 hours of first becoming aware of the SAE. The investigator must complete an SAE form and include a detailed description of the SAE, as well as other available information pertinent to the case (e.g., hospital records, autopsy reports, and other relevant documents). The investigator will keep a copy of this SAE report form on file at the study site.

The investigator, after thorough consideration of all facts that are available, must include an assessment of causality of the SAE to SM in the report to the Sponsor or designee.

SAEs should be followed until resolution or until no further/additional information can be obtained regarding the event. Follow-up information, or new information available after the initial report, should be actively sought and reported to the Sponsor or designee, as it becomes available, using the SAE report form.

The drug safety contact for SAE reporting is:

If the email was not successfully transmitted and a second attempt is unsuccessful, contact the study site CRA.

7.2.10 Other Events Requiring Immediate Reporting

The investigator must report a pregnancy that occurs in a subject during the study to the Drug Safety Team within 24 hours of first becoming aware of the event.

Subjects who become pregnant during the study should be discontinued from SM immediately. A pregnancy should be reported on a pregnancy report form. The investigator should discuss the case with the Medical Monitor, and the investigator must follow any pregnant subject until 3 months after the child is born. Any AEs concerning the pregnancy of the subject during pregnancy or the child after birth must be documented and reported to the Sponsor or designee.

Acute suicidal crisis or clinically significant suicidal behavior or ideation should be reported to the Drug Safety Team within 24 hours of first becoming aware of the event.

7.2.11 Sponsor Responsibilities for Reporting Serious Adverse Events

The Sponsor or designee will inform the investigator and regulatory authorities of reportable events, in compliance with applicable regulatory requirements, on an expedited basis (i.e., within specific timeframes). For this reason, it is imperative that the study site submit SAE information to the Sponsor or designee in the manner described above.

The investigator must comply with the applicable regulatory requirements related to the reporting of SAEs to the Institutional Review Board (IRB). The investigator must also submit the safety information provided by the Sponsor to the IRB unless the country legal regulation requires that the Sponsor should be responsible for the safety reporting to the IRB.

It is the responsibility of the Sponsor to notify the investigator, in a written Investigational New Drug Safety Report, of any SADR that is both serious and unexpected. The Sponsor will also notify the investigator of any findings from other sources (other studies, animal, and in vitro testing, etc.) that suggest a significant risk for human subjects. Such findings will typically lead to safety-related changes in the study protocol, ICF, and/or IB.

7.2.12 Clinician-Administered Dissociative States Scale

The CADSS is a 23-item, clinician-administered scale that measures present-state dissociative symptoms ([Bremner, 1998](#)).

The subjective component of this scale consists of items administered by the clinician who begins each question with anchors and then reads the item to the subject. The subject then rates items on a 4-point Likert scale: 0=not at all, 1=mild, 2=moderate, 3=severe, and 4=extreme, with a total score ranging from 0 to 92.

The scale is a ClinRO administered by a qualified rater at screening, days 1, 7, and 10 of the evaluation period, and during the safety follow-up phone call.

7.2.13 Brief Psychiatric Rating Scale

The BPRS is one of the most widely used instruments enabling the clinician to quickly gather information about the possible presence and severity of various psychiatric symptoms ([Zanello 2013](#)). Varying in the number and type of symptoms assessed, clarity of anchor point definitions and administration and rating instructions, the BPRS exists in various forms. Originally in the early 1960s, the BPRS was developed as a 16-item instrument ([Overall 1962](#)), that was later extended to 18 items and was used for many years ([Overall 1967](#)). In order to increase its sensitivity to psychotic and affective disorders as well as to be used with patients living in the community, the BPRS was expanded to 24 items (Version 2, [Lukoff 1986](#)). In its latest version (Version 4.0), the manual of administration of the 24-item BPRS+ ([Ventura 1993](#)) not only offers a more detailed semi-structured interview containing more probe questions for each symptom but also provides supplementary rules for the rating (e.g., delusions) with better-defined anchor points.

The version used for this study is adapted from the original BPRS+. The scale is comprised of 4 items assessing a subject's experience of psychosis, often referred to as positive symptoms of Suspiciousness, Hallucinatory Behavior, Unusual Thought Content, and Conceptual Disorganization. Of the 4 items assessed, the first 3 items are based on questions asked by the clinician to the subject. Conceptual Disorganization is a clinician-rated item based on observation of a subject's behavior and speech during the assessment.

The scale is a ClinRO administered by a qualified rater at screening, days 1, 7, and 10 of the evaluation period, and during the safety follow-up phone call.

7.3 Treatment-Emergent Suicidal Ideation

Prospective assessment of suicidal ideation and suicidal behavior is a mandatory part of the safety evaluations for any drug developed for a psychiatric indication ([US Food and Drug Administration 2012](#)). In this study, the initial evaluation of subjects will be conducted prior to enrollment to assess lifetime suicidal ideation and to identify subjects who must not participate in the study due to a pre-existing suicidality risk. The assessment will then be repeated at each

subsequent clinic visit as well as during the safety follow-up phone call to monitor the occurrence of new suicidal and self-injurious tendencies.

7.3.1 Columbia Suicide Severity Rating Scale

Assessment of suicidal ideation and behavior will be conducted using the C-SSRS (Baseline/Screening Version and Since Last Visit Version) ([Posner 2011](#)). The C-SSRS is an FDA-recommended, prospective assessment instrument that directly classifies suicidal ideation and behavior events into 11 preferred categories, including 5 levels of suicidal ideation, 5 levels of suicidal behavior, and the category of self-injurious behaviors with no suicidal intent.

The instrument has been validated and used successfully in adult patients with various psychiatric disorders that do not involve cognitive impairment. The C-SSRS outcomes that can be used for clinical management and safety monitoring are suicidal lethality rating, suicidal ideation score, and suicidal ideation intensity rating.

The scale is a ClinRO administered by a qualified rater at screening, days 1, 4, 7, and 10 of the evaluation period, and during the safety follow-up phone call.

7.3.2 Suicide Risk Management Plan

The protocol procedures related to clinical care of patients with treatment-emergent suicidal ideation and behavior must be implemented to ensure proper management of the event and protection of subjects' safety. If a disclosure of suicidal ideation is revealed as part of the C-SSRS questionnaire or when a subject spontaneously expresses that he/she may be a threat to him/herself, the study team should be prepared to quickly evaluate the event and to determine the appropriate course of action.

7.3.2.1 Assessment of Suicide Risk

Any indication of suicidal ideation should be evaluated as soon as possible by appropriately trained staff. The investigator is responsible for making the final judgment regarding potential suicide risk and the need for subsequent action.

Acute Suicidal Crisis

A person evaluated as being at high risk for suicide should be transferred to an immediate care facility. The investigator will guide intervention as clinically indicated and follow-up with the subject within 1 week and/or refer him/her to a qualified mental health professional.

Non-Acute Suicidal Risk

The investigator will conduct safety planning with a subject evaluated as being a non-acute risk for suicide and will follow up within 1 week.

Reference materials for subjects and caregivers should include lists of mental health organizations and professionals, outpatient behavioral services, local crisis and peer support groups, and suicide/crisis hotlines.

7.4 Clinical Measurements

7.4.1 Screening and Clinical Safety Laboratory Assessments

All clinical laboratory tests will be performed by a local laboratory as specified in the reference binder.

Details for collecting, handling, and shipping samples (including shipment addresses) will be detailed in a separate clinical laboratory manual. The Schedule of Events and Assessments (Table 1) shows the time points at which blood and urine samples will be collected. Table 3 lists the clinical laboratory tests to be performed.

Table 3: Clinical Laboratory Tests

Category	Parameter
Hematology	Red blood cell count, hemoglobin, hematocrit, platelet count, white blood cell count with differential
Chemistry	Electrolytes: chloride, phosphate, potassium, sodium
	Liver function tests: alkaline phosphatase, aspartate aminotransferase, alanine aminotransferase, total bilirubin, direct bilirubin
	Renal function parameters: blood urea nitrogen, serum creatinine ^a
	Other: glucose, calcium, albumin, total protein, bicarbonate, thyroid-stimulating hormone, free triiodothyronine (T3), free thyroxine (T4), follicle-stimulating hormone (postmenopausal females only)
Serology ^b	HBsAg, HCV Ab, HIV 1/2 Ag/Ab
Urinalysis	Microscopic examination ^c , pH, specific gravity, protein, glucose, ketone, occult blood, white blood cell count, nitrites, bilirubin, urobilinogen
Standard Urine Drug Screen ^d	Amphetamines ^e , barbiturates, benzodiazepines ^e , buprenorphine, cocaine, ecstasy, ethanol, methadone, methamphetamine ^e , methylphenidate ^e , opiates, oxycodone, phencyclidine, propoxyphene, tricyclic antidepressants, tetrahydrocannabinol (cannabinoids)
POC ^f Urine Drug Screen	Amphetamines ^e , barbiturates, benzodiazepines ^e , buprenorphine, cocaine, ecstasy, methadone, methamphetamine ^e , opiates, oxycodone, phencyclidine, propoxyphene, tricyclic antidepressants, tetrahydrocannabinol (cannabinoids)
Breathalyzer ^f	Ethanol
Pregnancy test (FOCP only) ^g	Human chorionic gonadotropin

ADHD = attention-deficit/hyperactivity disorder; FOCP = females of childbearing potential; HBsAg = hepatitis B surface antigen; HCV Ab = hepatitis C antibody; HIV = human immunodeficiency virus 1/2 antigen/antibody; POC = point-of-care

a. Glomerular filtration rate will be calculated using the Chronic Kidney Disease Epidemiology Collaboration equation at screening only.

b. Confirmatory serology testing for positive HIV, hepatitis B and HCV at screening will be performed.

c. A microscopic examination will be performed on abnormal findings unless otherwise specified.

d. Standard urine drug screen will be performed at screening. A positive test must be confirmed against medical history and concomitant medications.

- e. Amphetamine, methamphetamine, and methylphenidate (methylphenidate will not be tested during the treatment period) positive tests are allowed only for subjects diagnosed with ADHD confirmed by a prescription record. Benzodiazepine positive test is allowed if used for insomnia.
 - f. POC urine drug screen together with the breathalyzer will be performed at baseline (Day 1) and all post-baseline visits (days 4, 7, and 10).
 - g. A serum pregnancy test will be performed at screening; a urine pregnancy test will be performed on days 1, 4, 7, and 10.

7.4.2 Vital Signs and Weight

Vital signs measurements (includes orthostatic blood pressure/pulse rate, respiratory rate, and oral temperature) and body weight will be obtained at the time points shown in the Schedule of Events and Assessments ([Table 1](#)). Orthostatic blood pressure and pulse rate should be measured after the subject has been sitting for 5 minutes and again within 3 minutes of subject standing. Vital sign measurements may be taken at any other time, as deemed necessary by the investigator.

7.4.3 Physical Examinations and Height

Physical examinations and measurement of height will be obtained at the time points shown in the Schedule of Events and Assessments ([Table 1](#)). The complete physical examination conducted at screening and baseline visits will include assessments of all body systems except genitourinary. Any abnormal findings during screening will be recorded as medical history and any clinically significant abnormal findings following the first administration of SM on Day 1 will be recorded as TEAEs. Only changes from baseline observations will be noted during the brief physical examination at the EOS.

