- The follow-up assessments will be performed through a safety follow-up phone call. The safety follow-up phone call will occur approximately 5 days after the last administration of SM.
- AEs reported during screening will be recorded as part of the subject's medical history.
- A complete physical examination will be performed at screening and baseline visits; a brief physical examination will be performed at EOS/ET.
- Vital signs measurements include orthostatic blood pressure/pulse rate, respiratory rate, and oral temperature. Orthostatic blood pressure and pulse rate should be measured after the subject has been sitting for 5 minutes and again within 3 minutes of subject standing.
- ECGs should be performed prior to blood draws.
- Serology tests include human immunodeficiency 1/2 antigen/antibody, hepatitis B surface antigen, and hepatitis C virus antibody.
- A standard urine drug screen will be performed at screening and point-of-care urine drug screen together with the breathalyzer will be performed at baseline (Day 1) and all post-baseline clinic visits (days 4, 7, and 10).
- On days 2, 3, 5, 6, 8, and 9, the HAM-D₆ questionnaire will be administered remotely by telephone.
- SAEs will be captured from the time of ICF signing, and AEs will be captured following the first administration of SM and continue through the FPC.
- Seven total blood samples will be collected for measurement of BDNF concentrations: 3 pre-dose collections on days 1, 4 and 7; 3 post-dose collections 4 hours after SM administration on days 1, 4, and 7; and 1 collection on Day 10.
- Subjects will take their SM in the clinic.
- Subjects will receive a paper ADT adherence diary at screening and document the day of each dose of their ADT throughout the study. Subjects will bring their ADT adherence

diaries to each clinic visit for review of subject compliance.

m. ADT will not be provided by the Sponsor. Subject's ADT will have started and have been stable for at least 6 weeks prior to screening and will continue through the safety follow-up phone call.

Table 2: Detailed Schedule of Timed Assessments (Window)

Study Day	Clinic Visit Number	Location	Time ^a		HAM-D ₆ ^b	MADRS ^b	CGI-S	BDNF ^c
1	2	Clinic	Pre-dose		X (-60 min)	X (-60 min)	X (-60 min)	X (-60 min)
			1 hour					
			2 hours		X (±30 min)			
			4 hours		X (±30 min)	X (±30 min)		X (±30 min)
			8 hours		X (±30 min)			
2	–	Home	24 hours		X (±2 h) ^e			
3	–	Home	48 hours		X (±2 h) ^f			

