8.13 Safety Analysis

Safety analysis is a secondary analysis and will be performed using the safety population. Summaries will be presented for TEAEs and data from the clinical laboratory tests, vital sign measurements, body weight, ECGs, C-SSRS, CADSS, and BPRS+. Physical examination results will be listed by subject.

TEAEs: The incidence rate for all TEAEs will be summarized for each System Organ Class (SOC) and Preferred Term (PT). The severity of the TEAEs, the relationship to SM, SAEs, AEs leading to SM withdrawn, and deaths will be summarized for each SOC and PT. Common TEAEs ($\geq 5\%$) will be summarized by PT. The verbatim descriptions with Medical Dictionary for Regulatory Activities coded SOCs and PTs for all AEs will be contained in the subject data listings.

Clinical Laboratory Values, Vital Sign Measurements, and Body Weight: Both actual values and change from baseline and shift from baseline will be summarized for clinical laboratory values, vital sign measurements, and body weight.

ECG results will be summarized using descriptive statistics (for quantitative ECG parameters) and frequency tables (for qualitative ECG parameters, including the overall ECG finding).

C-SSRS outcomes will be summarized using number and percentage of subjects by categories for suicidal ideation only, suicidal behavior only, and suicidality (ideation and behavior combined).

CADSS outcomes will be summarized using descriptive statistics.

BPRS+ outcomes will be summarized using descriptive statistics.

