8.6. Physical Examination

The number and percentage of subjects with Normal, Abnormal not Clinically Significant, Abnormal Clinically Significant and Not Done findings from CRF page will be summarized descriptively and flagged in the listings. Data listings will be provided.

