9. CHANGES FROM THE PROTOCOL

No changes to any planned analyses from the protocol.

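### SAP 8.6 tabulates absolute physical examination status, but the Day 10 examination records only changes, so its counts are not comparable with baseline and could read as a false improvement

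*Protocol*

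**What the plan says.** Four provisions bear on this point.

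- **What is examined.** Table 1 of the protocol schedules a physical examination at screening, Day 1 and Day 10 (EOS/ET). Its footnote sets the scope: "A complete physical examination will be performed at screening and baseline visits; a brief physical examination will be performed at EOS/ET".
- **What is recorded.** Protocol 7.4.3 limits the last examination: "Only changes from baseline observations will be noted during the brief physical examination at the EOS". It also says "Any abnormal findings during screening will be recorded as medical history", and that "any clinically significant abnormal findings following the first administration of SM on Day 1 will be recorded as TEAEs".
- **What the protocol plans to report.** Section 8.13: "Physical examination results will be listed by subject". No table is mentioned.
- **What the SAP plans to report.** Section 8.6 summarises "The number and percentage of subjects with Normal, Abnormal not Clinically Significant, Abnormal Clinically Significant and Not Done findings from CRF page", along with listings. Section 9 then states: "No changes to any planned analyses from the protocol".

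Physical examination findings are a named safety endpoint in protocol 3.2.4, and the SAP 8.6 summary is the only table planned for them.

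**The concern.** A status table needs each subject's current state at each examination. A change-only record does not supply it. A subject whose baseline abnormality is still present and unaltered on Day 10 has, under 7.4.3, nothing to note. SAP 8.6 has no category for unchanged and no mapping rule. Protocol 8.3 imputes no safety data other than AE and medication dates, so nothing in the plan carries the Day 1 status forward.

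Day 1 therefore contributes full status from a complete examination, and Day 10 contributes changes from a brief one. Put side by side, the abnormal count could fall with no subject having improved. In an uncontrolled study there is no comparator arm in which the same artefact would show up and alert the reader.

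**Working it through.** The plan states no figure for physical examination findings, so there is nothing to reproduce. The check has two parts.

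**1. Following one subject through the text.** Take a subject with an abnormality at the complete Day 1 examination that is unchanged on Day 10.

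| Handling on Day 10 | Consistent with 7.4.3? | Result in the SAP 8.6 table |
|---|---|---|
| Nothing noted, coded Normal | Yes | Counted as normal |
| Nothing noted, coded Not Done | Yes | Visible as not done, not counted as abnormal |
| Nothing noted, left blank | Yes | Missing, may leave the denominator |
| Coded as no change | Yes | No cell for it in SAP 8.6 |
| True current status entered | Goes beyond a literal reading | Counted correctly |

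Under every literal reading the subject is not counted as abnormal. The table is right only if the site records more than 7.4.3 asks for, or if an unwritten rule is applied. SAP 3.1 keeps unscheduled measurements out of summary tables, so the post-baseline part of the table rests on the Day 10/ET record alone.

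**2. Size of the possible distortion (illustration).** Inputs:

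- N = 50 or 40: the approximate enrolled and completed numbers in protocol 8.2, used only for scale.
- Share abnormal at baseline, b = 10%, 20% or 40%: assumed, since the documents give no rate.
- All baseline abnormalities persist unchanged, U = b × N: assumed.
- New abnormalities on Day 10 in previously normal subjects, W = 0 or 2: assumed.

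Formulas:

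- True Day 10 abnormal % = (U + W) / N
- Day 10 abnormal % if unchanged is coded Normal = W / N
- Apparent change from baseline = (W − U) / N

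| N | b | U | W | True Day 10 | As tabulated | Apparent change |
|---|---|---|---|---|---|---|
| 50 | 10% | 5 | 0 | 10% | 0% | −10 points |
| 50 | 20% | 10 | 0 | 20% | 0% | −20 points |
| 50 | 40% | 20 | 0 | 40% | 0% | −40 points |
| 50 | 10% | 5 | 2 | 14% | 4% | −6 points |
| 50 | 20% | 10 | 2 | 24% | 4% | −16 points |
| 50 | 40% | 20 | 2 | 44% | 4% | −36 points |
| 40 | 20% | 8 | 0 | 20% | 0% | −20 points |
| 40 | 20% | 8 | 2 | 25% | 5% | −15 points |

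The result depends on the coding. For N = 50, U = 10 and W = 2:

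- True status entered: 12/50 = 24%, no distortion.
- Unchanged coded Normal: 2/50 = 4%.
- Unchanged coded Not Done and kept in the denominator: 2/50 = 4% abnormal, with 10 subjects visibly not done.
- Only the 10 unchanged abnormal subjects left out: 2/(50 − 10) = 5%.
- Every subject with nothing noted left out, including the unchanged normals: 2/2 = 100%, an apparent worsening.

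**The case against.** The strongest reply is that the CRF page is not in the documents, and SAP 8.6 takes its categories from that page. This suggests that the page asks for an overall status. The restriction in 7.4.3 may then govern only which findings are described, and the table would be correct. SAP 8.6 also does not say that the table is by visit or set against baseline, whereas the laboratory, C-SSRS and CADSS/BPRS+ sections do ask for by-visit summaries. As the last example above shows, the direction of any distortion is not fixed. SAP 3.1 also requires a footnote where a denominator differs from the column header.

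All of this stands, and it limits the point to what could happen. It does not remove the gap: the text tells sites to record one thing and the analysis to count another, and nothing links the two. The undeclared move from a listing to a table can be verified without the CRF.

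A reader might also infer two stronger things that the documents do not support.

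- **That new findings would be hidden.** New findings are changes, which is exactly what 7.4.3 keeps, and they appear in the Day 10 count in every example above. Clinically significant ones also become TEAEs, tabulated by SOC and PT under SAP 8.1.
- **That 7.4.3 conflicts with the TEAE definition**, because it does not say that a clinically significant finding must be new or worse. Protocol 7.2.5 and SAP 8.1 already require onset on or after the first dose, or worsening. At most the sentence could be clearer.

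**Conclusion.** The mismatch is real and modest. Read literally, protocol 7.4.3 does not supply the data that SAP 8.6 tabulates, and SAP 9 does not acknowledge that a table has been added where the protocol plans a listing. Day 10 status counts are then not comparable with baseline, and the difference in scope between a complete and a brief examination adds to this.

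If unchanged abnormalities are coded Normal and the table is shown by visit, the spurious fall equals the share of subjects with an unchanged baseline abnormality. That is 10 to 40 percentage points over the assumed range, with no new findings. If sites enter true status, it is zero. The documents do not settle which applies, so it would be wrong to say that the table must show an improvement.

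The consequence is a potentially misleading descriptive safety table, not a lost harm signal. Screening abnormalities remain in medical history, new clinically significant findings remain in the TEAE tables, and individual results remain in the listings.

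**What to change.** In SAP 8.6:

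- Summarise baseline status on its own, using the existing four categories.
- For Day 10/ET, replace absolute status with n (%) of examined subjects who have at least one new or worsened finding, split by clinical significance. Report the number not examined separately.
- State that the same rule applies to ET, since 7.4.3 names only EOS for change-only recording while Table 1 treats the two visits together.

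In SAP 9, declare that a physical examination table has been added to the listing planned in protocol 8.13.

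Carrying the Day 1 status forward where no change is noted would be a weaker choice. A brief examination may not cover every system seen in the complete one, so the carried status could describe something that was not examined.

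The cost is SAP wording and one table shell. No further assessments are needed. Before finalising, check that the CRF page separates examined with no change from not done, because the new denominator depends on it.
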